2.11 Dietary Restrictions

Due to potential food-drug interactions for many commonly used medications, grapefruit, grapefruit juice, Seville oranges, and any products that contain Seville oranges or grapefruit should be avoided when possible.

2.12 Treatment Compliance

The prescribed dosage, intervals between doses, and mode of administration, e.g., after meals, intact tablet (not crushed) may not be changed without direction by the investigators. They must be recorded in the eCRFs.

The patient will be provided with a drug log to record date and time of administration, time of meal prior to administration, AEs, and missed doses. To verify compliance, the patient will be instructed to bring the drug log and study drug bottles (including any empties) to appointments scheduled for Day1 of each cycle starting with Cycle 2 for reconciliation.

At each visit when study medication is dispensed previously dispensed study drug count will be confirmed by the investigator, or authorized designee, and compliance assessed prior to dispensing new study medication.

Patients exhibiting poor compliance as assessed by tablet counts and not following dosing schedules should be counseled on the importance of good compliance to the study dosing regimen. Noncompliance to drug amount is defined as taking <75% or >125% of study medication during a cycle. Noncompliance to dosing interval is defined as more than 2 occurrences of <3 days between doses during a cycle, for example, 1 or 2 days between doses #3 and #4 instead of 3 or 4 days according to a BIW schedule. If in the opinion of investigator a patient is unable to follow instruction, study treatment should be discontinued.

2.13 Study Medication Accountability

A clinical supplies shipment/receipt verification form will be enclosed with each study drug shipment. The site pharmacist who receives the shipment should complete this form and clinical research associate should collect a copy of the form at each pharmacy visit. If instead of the shipment/receipt verification form, a packing list is enclosed with the shipment, acknowledgment of the study drug receipt should be done through the IWRs system by the site pharmacist or authorized designee.

The investigator, or authorized designee, must maintain a complete and accurate record of the receipt and distribution of all study medication using the Drug Accountability Form. These forms will be described in detail in the pharmacy manual and must be available for inspection at any time.

All study medication supplies should be accounted for at the termination of the study, and a written explanation provided for any discrepancies. All unused study medication supplies and

packaging materials are to be inventoried and returned to the local depot by the investigator, or authorized designee. The investigator, or authorized designee, is not permitted to return or destroy unused clinical drug supplies or packaging materials unless authorized by the sponsor or delegate(s).

3.0 STUDY ASSESSMENTS

3.1 Efficacy

3.1.1 Primary Efficacy Endpoint

The primary efficacy endpoint is to establish the ORR, defined as the proportion of patients with tumor size reduction of a predefined amount and for a minimum time period, evaluated by using the revised criteria for response assessment in lymphoma [[Cheson 2014](#)] (see Section 9.4).

Tumor assessments will be performed by imaging modalities. CT, magnetic resonance imaging, or PET scanning may be used to evaluate lesions in the neck, chest, abdomen, and pelvis; and as a baseline evaluation for patients who may have brain metastases. The PET-CT is encouraged to be performed from baseline. However, when CT is the routine method to monitor patients according to hospital standard of care, PET-CT is not required. Evaluation of nodal lesion and extranodal lesion will be performed according to the revised criteria for response assessment in lymphoma [[Cheson 2014](#)] (see Section 9.4). Skin lesions are non-target lesions. Their response will be assessed according to mSWAT, and contribute to overall response determination.

Tumor response based on imaging studies will be confirmed with central review by independent radiologists at end of study prior to final efficacy analysis. The dates of PR, CR and PD will be assessed as applicable. Initial review will be performed by one independent radiologist. If the results differ from those reported by the investigators based on local radiology findings, a second independent radiologist will be asked to adjudicate by way of assigning the final disease response to the determination made by either the investigators or independent radiologist. The overall efficacy review will be done by independent oncologist for final efficacy analysis.

3.1.2 Secondary Efficacy Endpoints

The secondary efficacy measures are:

- ORR by disease subtype
- Median duration of PFS defined as the time from the first dose of study medication to objective tumor progression or death.
- Median DOR defined as the time from the first observation of tumor response to PD.

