Treatments:	
Study drug is to be taken after any regular meal twice weekly, each dose separated by 3-4 days. Treatment will continue until PD in the absence of unacceptable toxicity, whichever is earlier. Study drug treatment will be completed when the commercial product of HBI-8000 is available at the study sites after the PTCL approval.

Efficacy Data:	
Response and progression for PTCL will be evaluated according to the revised criteria for response assessment in lymphoma [Cheson 2014]. To be included in final efficacy analyses, the histopathology diagnosis of disease will be verified by Central Pathology Review, and disease response will be confirmed by Independent Radiology and Independent Overall Efficacy Review.

Safety Data:	
All patients who receive at least one dose of HBI-8000 will be evaluable for safety. Adverse event severity (grade) will be defined according to Common Terminology Criteria for Adverse Events (CTCAE) Version 4.03. Serial ECGs and clinical laboratory tests will be collected to evaluate safety and potential toxicity. Laboratory and other tests, as appropriate to the clinical situation, may be obtained more frequently than stipulated in the schedules of events.
 
All reported AEs will be collected, evaluated and coded using Medical Dictionary for Regulatory Activities (MedDRA).

Pharmacokinetics data from selected sites:	At sites participating in population PK assessments, blood samples for plasma HBI-8000 measurement will be taken on Day 1 of Cycle 1 at pre-dose, 1 h (\pm 15 min), 2 h (\pm 15 min), 3 h (\pm 15 min), 4 h (\pm 15 min), 5 h (\pm 30 min), 7 h (\pm 30 min), 24 \pm 1 h, 48 \pm 1 h and 72 \pm 1 h. On Day 1 of Cycle 2 (e.g., C2D1) PK samples will be taken at pre-dose and 1 h (\pm 15 min), 2 h (\pm 15 min), 3 h (\pm 15 min), and 4 h (\pm 15 min). On Day 1 of Cycles 3 to 6, only pre-dose PK samples will be taken.
Statistical Procedures:	
Statistical analysis for all safety, efficacy, and PK parameters will be primarily descriptive in nature. Categorical variables will be summarized by frequency distributions (number and percentages of patients), continuous variables will be summarized by mean, standard deviation, median, minimum, maximum, and time-to-event variables will be summarized using Kaplan-Meier methods and figures for the estimated median time. A formal statistical analysis plan will be completed prior to database lock and any study-related analyses.	

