2.6 Study Procedures Overview

Patients may be treated in this study as long as they receive clinical benefit (stable disease or a response) in the absence of unacceptable toxicity. Disease progression would be determined by investigators based on local radiology findings and clinical judgement. No independent radiology review is required prior to designation of PD and treatment discontinuation. Independent Radiology Review and Independent Overall Efficacy Review will be performed for final efficacy analyses at the completion of this study.

To ensure patient safety, a data safety monitoring board (DSMB) will convene to review the cumulative safety profiles of study patients at following milestones: first 6 patients completing at least 1 cycle, 12, 18, 30 patients have been treated for at least 1 cycle and at end of treatment Phase of the study. Based on the observed safety, dose and regimen of ongoing treatment may be modified as needed. For all patients, weekly safety laboratory tests will be obtained during the first 28 days and closely monitored for safety signals, especially for neutropenia and transaminase elevation.

It is estimated that each patient will be on study for up to 42 months after enrollment. Assuming that 24 months are needed to meet accrual target, the study period would be of 66 months to allow efficacy and safety determination. After study drug is discontinued, patients will be followed as described in Sections 2.6.4 and 2.6.5.

Patients will be screened by the study site investigator prior to entry into the study. Patients will receive a detailed explanation of the study design, and the potential risk/benefit of treatment will be disclosed to patients prior to the screening process. Only eligible and consenting patients will be enrolled into the study. Local histopathology report could be used to consent patient. Central pathology review will be completed before efficacy analysis. The investigator will maintain a pre-screening log to record all patients prior to screening.

Similarly, local radiology reports on disease status will guide investigator's decision on study treatment, including discontinuation. At end of the study, tumor response of each patient will be reviewed by independent radiologists and oncologists in a blinded fashion to obtain best response, dates of response and progression. The data from independent and local assessment will be analyzed in parallel in final study report.

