2.6.4 End of Treatment Safety Follow-up Visit

All patients receiving at least one dose of HBI-8000 and discontinuing treatment for any reason except death will be assessed 30 (\pm 3) days after the last dosing of study drug, before the initiation of new cancer treatment or before the initiation of administration of commercial product of HBI-8000, whichever is earlier. Any patient for whom study treatment has been discontinued should complete study procedures listed in the EoT visit. At EoT safety visit, evaluations will include physical examination, vital signs, body weight, ECOG performance

status, hematology, blood chemistry, urinalysis, pregnancy test (if applicable), ECG, and assessment of any ongoing adverse events. If a patient discontinues study treatment before PD is recorded, and if the last tumor assessment was >30 days earlier from the EoT visit, tumor assessment should be performed at EoT. In these patients, further tumor assessments are to be performed approximately every 3 months \pm 2 weeks until PD or the start of new cancer therapy whichever occurs first, unless consent to study participation is withdrawn or by completion of the whole study. If subjects cannot visit at site for this examination due to COVID-19 situation, investigators can skip the examination, and the assessment is to be performed approximately every 6 months \pm 2 weeks. In this case, the investigator should document that fact in the medical record.

Patients with HBI-8000-related AEs of Grade ≥ 2 observed at the EoT visit should be followed-up and assessed monthly (phone calls/clinic visits) until the AEs have resolved to Grade ≤ 1 or are determined to be chronic, or patient receives other anti-cancer therapy.

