5.0 STATISTICS

5.1 General Statistical Considerations

Protocol HBI-8000-203 is an open-label, Phase 2b pivotal study evaluating HBI-8000 for regulatory approval in Japan and South Korea for the indication of relapsed or refractory PTCL. The main analysis will be conducted for the purpose of regulatory submission of this product. The data cut-off (DCO) for the main analysis is set at the time when the last patient completes at least one post-efficacy assessment. The eCRF data by the DCO needs to be cleaned to have no unresolved queries. All independent reviews (including the Central Pathology Review, the independent radiological review, the Independent Overall Efficacy Review and review by the Data Safety Monitoring Board) by the DCO need to be completed before the main analysis. The data after the main analysis will be provided at the end of the study as a supportive material.

Statistical analysis for all safety, efficacy, and PK parameters will be primarily descriptive in nature. Categorical variables will be summarized by frequency distributions (number and percentages of patients), continuous variables will be summarized by mean, standard deviation, median, minimum, maximum, and time-to-event variables will be summarized using Kaplan-Meier methods and figures for the estimated median time.

All analyses, summaries, and listings will be performed using SAS software (version 9.3 or higher)

A detailed methodology for summary and statistical analysis of the data collected in this trial will be documented in a Statistical Analysis Plan (SAP) that will be dated and maintained by HUYABIO. The SAP may modify the plans outlined in the protocol; however, any major modifications of the primary endpoint definition and/or its analysis will also be reflected in a protocol amendment.

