5.9 Efficacy Analysis

The efficacy endpoints are the following:

Primary Endpoint:

- ORR(CR + PR)

Secondary Endpoint:

- ORR by disease subtype (see Section 2.5.1)
- Median duration of PFS
- Median DOR

Exploratory Endpoint

- Median duration of OS

Response rate endpoints (ORR and ORR by disease subtype) will be summarized by number and percentage of patients meeting the definition of ORR along with the corresponding exact 95% CI. Tumor response as assessed by imaging studies will be adjudicated by independent radiology reviewers. Tumor lesions, such as skin lesion, that cannot be monitored by imaging studies will be determined by independent oncology reviewers and contributed to overall disease response assessment. Both investigators reported and independently adjudicated outcomes will be reported. Primary analysis will be based on results from imaging studies and clinical data confirmed by Independent Central Review. Results from investigator assessment will also be reported. In addition, the ORR will be analyzed according to histology subtypes of PTCL. The subtypes reported by Central pathology review for each patient will be used for such analysis.

Time-to event endpoints (PFS, DOR, and OS) for entire study population will be summarized by Kaplan-Meier methods (median, 95% CI, number of events, number censored and Kaplan-Meier figures).

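### Section 3.1.2 ends duration of response at progression only, while PFS in the same list ends at progression or death, so a responder's death without documented progression is not a DOR event

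*Combined protocol and SAP*

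**What the plan says.** Section 3.1.2 of the protocol (version 6.0) holds the only definition of DOR: "Median DOR defined as the time from the first observation of tumor response to PD". The bullet directly above it defines PFS as the "time from the first dose of study medication to objective tumor progression or death". The synopsis and Sections 2.3 and 5.9 name DOR without defining it. Section 3.5.4 has the independent oncologists assign dates of response and of progression, and does not mention death.

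Section 5.9 says that PFS, DOR and OS "will be summarized by Kaplan-Meier methods (median, 95% CI, number of events, number censored and Kaplan-Meier figures". It gives no event rule and no censoring date.

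On timing, Section 5.1 states: "The data cut-off (DCO) for the main analysis is set at the time when the last patient completes at least one post-efficacy assessment". Later data are supportive and come at the end of the study.

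Detailed methods are left to a separate SAP. The synopsis says: "A formal statistical analysis plan will be completed prior to database lock and any study-related analyses". Section 5.1 lets the SAP modify the protocol's plans, with the limit that "any major modifications of the primary endpoint definition and/or its analysis will also be reflected in a protocol amendment". The text of that SAP is not in the file.

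**The concern.** Two time-to-event endpoints in one list treat death differently. A responder who dies without documented progression has a PFS event but no DOR event. With Kaplan-Meier applied as written, that death is most naturally handled as censoring. Death ends a response, so it is a competing event and not a loss of information. The reported median would then describe time to progression as if such deaths did not occur, while readers will take it as the time until a response ends.

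Section 5.1 calls the study pivotal for approval in Japan and South Korea, and in a single-arm study DOR is what tells the reader how long the responses last. Few responders are expected and the main-analysis cut-off is early, so one or two such deaths could lengthen the median or leave it not reached.

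**Working it through.** The documents give no figure for DOR, so there is none to reproduce.

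**1. Direction for the endpoint as defined.** For each patient, time to progression ≥ min(time to progression, time to death). The progression-only time is never the shorter one.

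**2. Direction for the Kaplan-Meier median.** If deaths without progression are censored at the death date, both definitions have the same risk sets. At each time with n at risk, 1 − d_PD/n ≥ 1 − (d_PD + d_death)/n, so the progression-only curve never lies below the other and its median cannot be smaller.

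If such deaths are censored at an earlier last assessment, the risk sets differ and the guarantee is lost. Take three responders: progression at 5 and at 12, and a death at 10 last assessed at 2 (median = first time S ≤ 0.5).

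- Progression or death: S(5) = 2/3, S(10) = 1/3, median 10.
- Progression only, censored at death: S(5) = 2/3, S(12) = 0, median 12.
- Progression only, censored at 2: S(5) = 1/2, median 5.

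In simulations with 12 responders and assumed hazards, this reversal occurred in 0% to 0.2% of runs when imaging continued to death, and in about 9% to 11% when imaging was assumed to stop well before death.

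**3. Size under constant hazards.** Let f be the share of response endings that are deaths without progression; the documents do not give it. With total hazard λ, censoring the deaths leaves (1 − f)λ, so the ratio of true medians is 1/(1 − f):

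- f = 0.10: 1/0.90 = 1.11
- f = 0.20: 1/0.80 = 1.25
- f = 0.30: 1/0.70 = 1.43

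**4. Size at the main-analysis cut-off.** Inputs from the protocol:

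- Target ORR 30% and 40 evaluable patients (Section 5.2): 0.30 × 40 = 12 responders.
- Accrual (Section 2.6): "Assuming that 24 months are needed to meet accrual target".
- Cut-off shortly after the last patient's first assessment (Section 5.1), so follow-up after response is taken as uniform on 0 to 24 months.

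Assumptions: exponential response durations, each ending a death without progression with probability f, such deaths censored at the death date, and an assumed progression-or-death median of 5, 10 or 15 months. Each scenario had 100,000 runs. The expected share of responses still ongoing is (1 − e^(−24λ))/(24λ). At 10 months 24λ = 24 × ln 2/10 = 1.664, which gives 0.810/1.664 = 49%. At 5 and 15 months it is 29% and 60%.

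| Assumed median | Result (% of runs) | f = 5% | f = 10% | f = 20% |
|---|---|---|---|---|
| 10 months | medians coincide (or neither reached) | 87.5 | 76.3 | 57.6 |
| | progression-only alone not reached | 2.9 | 6.2 | 13.8 |
| | both reached, progression-only longer | 9.6 | 17.5 | 28.6 |
| 5 months | medians coincide | 81.6 | 66.0 | 41.7 |
| | progression-only alone not reached | 0.5 | 1.2 | 3.9 |
| 15 months | medians coincide | 91.8 | 84.2 | 70.9 |
| | progression-only alone not reached | 3.7 | 7.8 | 15.8 |

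At 10 months, where both medians were reached and differed, the typical ratio was 1.30 to 1.35. The progression-only median was shorter in no run, as step 2 requires for censoring at the death date.

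**5. Size with long follow-up.** With the 10-month median and an assumed 40 to 64 months of follow-up, the progression-only median alone is not reached in 0%, 0% and 0.1% of runs at f = 5%, 10% and 20%. It is longer in 27%, 47% and 74%.

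**The case against.** **The SAP may already deal with this.** The one-line definition may be shorthand that the SAP completes, and Section 5.1 allows the SAP to do so without an amendment, since DOR is not the primary endpoint. This stands: how DOR was or will be analysed cannot be known from the file. What remains is that the protocol does define the endpoint, and its wording leaves death out.

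**A reader might infer that the reported median can never be shorter than a progression-or-death median.** The documents do not support that for the estimate. It depends on censoring deaths at the death date, and no section states a censoring date.

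**A reader might point to the wider scan interval as a source of missed progression.** After treatment stops before progression, Section 2.6.4 says "further tumor assessments are to be performed approximately every 3 months", against 8 weeks on treatment, and that leaves some room for death without documented progression. The further widening to 6 months for COVID-19 is not relevant to the main-analysis cut-off on the planned dates: the tables of changes show that it entered with version 6.0 in July 2021, while the synopsis plans last patient in for 3Q 2018.

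**The number of such deaths may be small.** Scans may be brought forward when clinical signs appear (Section 2.6.3), investigators may use clinical judgement to call progression (Section 2.6), and the independent oncologists review clinical data (Section 3.5.4). All of these lower f. DOR is descriptive, with no test or threshold, and these deaths still count in PFS and OS. This stands, and it limits the weight of the point.

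**Conclusion.** The inconsistency is real and no current section repairs it. As defined, DOR can be longer but not shorter than a DOR that ends at progression or death. For the Kaplan-Meier median this holds if deaths without progression are censored at the death date; with an earlier censoring date the estimate can occasionally be shorter.

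The size is unknown. All figures above are illustrative and rest on an assumed f, assumed medians, constant hazards and assumed follow-up. Often the two medians would coincide, and if f is near zero nothing changes. The not-reached effect belongs mainly to the early cut-off. With long follow-up it all but disappears, and a longer median becomes the more frequent result.

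A reader might infer that the trial's DOR result is overstated. The documents do not support that: they give no count of such deaths, and the SAP may define DOR differently. The finding concerns the protocol wording. ORR, the sample size of 40 and the power are unaffected. It is worth correcting because the study is described as pivotal and the correction is nearly free.

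**What to change.** - In Section 3.1.2 or the SAP, define DOR as the time from first documented CR or PR to first documented progression or death from any cause, whichever is earlier.
- State the censoring date for responders without an event and, for the progression-only version, the censoring date for deaths without progression.
- Keep progression-only DOR as a labelled sensitivity analysis.
- If the main analysis has already been done, report the progression-or-death DOR beside it, labelled as added later.

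The cost is a few defining sentences and one extra Kaplan-Meier table. No new data are needed: deaths are collected under Section 2.6.5 and already count in PFS. Section 5.1 ties required amendments to the primary endpoint, so none is strictly needed. The downsides are that the median DOR may be somewhat shorter and that a change made after the main analysis must be shown as late.
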